## 3.1.1.2. Systemic Events Within 7 Days After Vaccination

Systemic events, including fever, fatigue/tiredness, headache, vomiting, diarrhea, muscle pain, and joint pain, are reported from Day 1 through Day 7 after vaccination, where Day 1 is the day of vaccination with RSVpreF or placebo. The derivations for the systemic events as described below will be handled similarly to the way that local reactions are handled for the presence for each participant, severity level, duration, onset day, and presence of systemic event on each and any day.

- 1. Presence (yes or no) of each systemic event on any day (Day 1 through Day 7) after vaccination.
- 2. Presence (yes or no) of any systemic event on any day (Day 1 through Day 7) after vaccination.

- 3. Maximum severity of each systemic event on any day (Day 1 through Day 7) after vaccination.
- 4. Maximum severity of any systemic event on any day (Day 1 through Day 7) after vaccination.
- 5. Duration of each systemic event after vaccination.
- 6. Onset day of each systemic event after vaccination.
- 7. Presence (yes or no) of each systemic event on each and any of the 7 days after vaccination.
- 8. Presence (yes or no) of any systemic event on each and any of the 7 days after vaccination.

The grading scale for systemic events is provided in the protocol. However, the derivation of severity of each systemic event on each day should be based on the maximum severity reported from the e-diary or AE CRF, if data are reported from both sources; or the e-diary alone if not reported from the AE CRF.

Fever is defined as a temperature of  $\geq 100.4^{\circ}\text{F}$  ( $\geq 38.0^{\circ}\text{C}$ ). The highest temperature for each day will be recorded in the e-diary. For reporting purposes, fever will be analyzed using the following temperature ranges:

- Mild ( $\geq$ 38.0 to 38.4°C from the e-diary or mild grade from the AE CRF);
- Moderate (>38.4 to 38.9°C from the e-diary or moderate grade from the AE CRF);
- Severe (>38.9 to 40.0°C from the e-diary or severe grade from the AE CRF);
- Grade 4 (>40.0°C from the e-diary or severe grade from the AE CRF, plus documented >40.0°C via CRF query or other sources).

If a participant reports a fever (or severity of fever) by accident, the correct temperature will be transcribed in a data handling memo to be included in the analysis, and the temperature that is confirmed as incorrect will not be included in the analysis.

#### 3.1.1.3. Adverse Events and Serious Adverse Events

Standard algorithms for handling missing AE dates and missing AE severity will be applied as described in the Pfizer vaccine data standard rules. Completely missing AE start dates will not be imputed.

The following derivations will be included for each participant:

- 1. Any AE reported within 1 month after vaccination If the AE started on the same day of vaccination, if the AE start time is before the vaccination time, this AE would not be counted. Otherwise, if the AE start time is missing or after the vaccination time, the AE is included. Any AE reported after the 1-month visit will not be included in the analysis.
- 2. Any related AE reported within 1 month after vaccination Similar to above except only a related AE is included (but excluding related reactogenicity reported within 7 days of vaccination) (Section 3.1.1).
- 3. Any immediate AE (AE start time is within 30 minutes after vaccination) reported after vaccination Only include AEs that started on the same day of vaccination and with nonmissing AE start time that is within 30 minutes of vaccination. If the immediate AE is a related reactogenicity event, this would not be included as an immediate AE.
- 4. Any severe AE reported within 1 month after vaccination.
- 5. Any life-threatening AE reported within 1 month after vaccination.
- 6. Any AE leading to study withdrawal after vaccination.
- 7. Any SAE reported throughout the study.
- 8. Any NDCMC reported throughout the study.
- 9. Any AESI reported throughout the study.

Variables 1 through 6 listed above will be derived from excluding any reactogenicity (but not excluding reactogenicity SAEs) reported in the AE CRF during the e-diary collection period. AESIs are flagged in the CRF.

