5.4. Screen Failures

Screen failures are defined as participants who consent to participate in the clinical study but are not subsequently enrolled in the study. A minimal set of screen failure information is required to ensure transparent reporting of screen failure participants to meet the CONSORT publishing requirements and to respond to queries from regulatory authorities. Minimal information includes demography, screen failure details, and any SAEs.

Individuals who do not meet the criteria for participation in this study (screen failure) may be rescreened under a different participant number.

5.5. Criteria for Temporarily Delaying Enrollment/Randomization/Administration of Study Intervention

The following conditions may allow a participant to be vaccinated once the conditions have resolved and the participant is otherwise eligible:

- Current febrile illness (temperature ≥38.0°C [≥100.4°F]) or other acute illness within 48 hours before study intervention administration.
- Receipt of any live vaccine within 28 days before study intervention administration. Receipt of any nonlive vaccine (including COVID-19 vaccines authorized for temporary or emergency use) within 14 days before study intervention administration.
- Anticipated receipt of any nonstudy vaccine within 14 days after study intervention administration at Visit 1 (before Day 15).
- Receipt of short-term (<14 days) systemic corticosteroids (equivalent of ≥20 mg/day of prednisone). Study intervention administration should be delayed until systemic corticosteroid use has been discontinued for at least 28 days. Inhaled/nebulized, intra-articular, intrabursal, or topical (skin, eyes, or ears) corticosteroids are permitted.

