8.10. Study Procedures

8.10.1. Visit 1 – Screening and Vaccination Visit (Clinic; Day 1)

Voluntary, written, study-specific informed consent (from the participant's parent[s]/legal guardian), and assent (from the participant, where appropriate), will be obtained before enrollment and before any study-related procedures are performed. Each signature on the ICD must be personally dated by the signatory. The investigator or his or her designee will also sign the ICD. A copy of the signed and dated ICD must be given to the participant/participant's parent(s)/legal guardian. The source data must reflect that the informed consent (and assent if appropriate) was obtained before participation in the study.

It is anticipated that the procedures below will be conducted in a stepwise manner; ensure that procedures listed **prior to administration of the investigational vaccine** are conducted prior to study vaccination. If screening and vaccination are not on the same day, all procedures listed as "on the day of and prior to vaccination" must be conducted prior to vaccination and on the day of the vaccination.

- Assign a single participant number using the IRT system.
- Obtain the participant's demography (including date of birth, sex, race, and ethnicity). The full date of birth will be collected to critically evaluate the immune response and safety profile by age.
- Obtain the participant's medical history of clinical significance.
- On the day of and prior to vaccination, perform a physical examination, including, at a minimum, measurement of height and weight, assessments of general appearance, lungs, cardiovascular system, and lymph node survey.
 - For participants 2 to <5 years of age: This procedure must be repeated on the day of and prior to vaccination if serostatus results will not be available on the same day as vaccination.
- On the day of and prior to vaccination, measure the participant's temperature as per usual clinical practice.
 - For participants 2 to <5 years of age: This procedure must be repeated on the day of and prior to vaccination if serostatus results will not be available on the same day as vaccination.

- All eligible participants will proceed to complete the vaccination visit.
- Record nonstudy vaccinations as described in Section 6.9.
- Obtain details of prohibited medication used as described in Section 6.9.1.

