## 2.2. Study Objectives, Endpoints, and Estimands

Type	Objective	Endpoint	Estimand
Primary Safety	To describe the safety and tolerability of RSVpreF at each dose level in children 5 to <18 years of age and children 2 to <5 years of age.	Local reactions (pain at the injection site, redness, and swelling). Systemic events (fever, vomiting, diarrhea, headache, fatigue/tiredness, muscle pain, and joint pain). AEs. SAEs. NDCMCs.	
 
In participants receiving 1 dose of study intervention at each dose level, for each age stratum:
 
The percentage of participants reporting local reactions within 7 days after vaccination.
 
The percentage of participants reporting systemic events within 7 days after vaccination.
 
The percentage of participants reporting AEs from vaccination through 1 month after vaccination.
 
The percentage of participants reporting SAEs throughout the study.
 
The percentage of participants reporting NDCMCs throughout the study.
 

Secondary Immunogenicity	To describe the immune responses elicited by RSVpreF at each dose level in children 5 to <18 years of age and children 2 to <5 years of age.	RSV A and RSV B NTs.	In participants in compliance with the key protocol criteria (evaluable immunogenicity population):  GMTs of NT for RSV A and RSV B 1 month after vaccination.  GMTs of NT for RSV A and RSV B before vaccination.  GMFRs of NT for RSV A and RSV B from before vaccination to 1 month after vaccination.

Туре	Objective	Endpoint	Estimand
Secondary Immunogenicity	To describe the cell-mediated immune response in children 5 to <18 years of age and children 2 to <5 years of age.	RSV F antigen–specific CD4+ T cells secreting IFNy. RSV F antigen–specific CD4+ T cells secreting IL-4.	
 
In participants in compliance with the key protocol criteria (evaluable immunogenicity population):
 
Median frequencies of RSV F antigen–specific CD4+ T cells expressing IFNγ before vaccination and 1 month after vaccination.
 
Median frequencies of RSV F antigen–specific CD4+ T cells expressing IL-4 before vaccination and 1 month after vaccination.
 

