## 2.3. Study Design

This is a Phase 1 open-label, age-descending, dose-finding study of the safety, tolerability, and immunogenicity of RSVpreF in RSV-seropositive children 2 to <18 years of age. Up to 120 participants will receive RSVpreF with up to 2 dose levels across 2 age strata (2 to <5 years and 5 to <18 years) and 2 risk substrata in the older group (5 to <18 years of age). Approximately 60 to 120 participants are expected to be enrolled.

Age Stratum (Years)	Number of Participants
2 to <5	~20/~20ª
5 to <18	~40/~40 a,b
Total	~60-120

- a. Up to 2 dose levels of RSVpreF (120  $\mu$ g and 60  $\mu$ g) will be tested in participants.
- b. Approximately 40 participants 5 to <18 years old will be enrolled, with ~20 healthy participants and ~20 participants with high-risk chronic medical conditions receiving each dose level.

For all participants enrolled, local reactions (redness, swelling, and pain at the injection site) and systemic events (fever, vomiting, diarrhea, headache, fatigue/tiredness, muscle pain, and joint pain) are collected from Day 1 (vaccination day) through Day 7 via the e-diary. AEs are collected from consent through the 1-month postvaccination visit. Additionally, AEs occurring up to 48 hours after blood draws that are related to study procedures are reported in the CRF. SAEs and NDCMCs will be collected from the time the participant's parent(s)/legal guardian provide informed consent through the duration of the study.

All participants 2 to <5 years of age must be seropositive. RSV serostatus will be determined before vaccination. Blood samples are collected before vaccination and at the 1-month postvaccination visit to assess RSV A and RSV B NT, as well as cell-mediated immune response through measuring RSV F antigen–specific CD4+ T cells secreting IFNγ and RSV F antigen–specific CD4+ T cells secreting IL-4.

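### The primary SAE and NDCMC rates (and the supplementary AESI rate) have no start at vaccination, so an event between consent and dose would count under the dose later received

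*SAP*

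**What the plan says.** SAP 3.1.1.3 lists nine derived variables.

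- Variables 1 to 6 (any, related, immediate, severe and life-threatening AEs, and AEs leading to withdrawal) are all worded as occurring after vaccination. For same-day events, variable 1 adds: "if the AE start time is before the vaccination time, this AE would not be counted". An event on that day with a missing start time is kept.
- Variables 7 to 9 read "7. Any SAE reported throughout the study", "8. Any NDCMC reported throughout the study" and "9. Any AESI reported throughout the study". They have no start and no pre-dose exclusion.

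The estimands show the same contrast. In SAP 2.2 the AE estimand runs from vaccination to 1 month, while the SAE estimand is "The percentage of participants reporting SAEs throughout the study" and the NDCMC estimand is parallel. SAP 2.2.1.1.3 and 2.2.1.1.4 repeat that wording.

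On collection, SAP 2.3 states: "SAEs and NDCMCs will be collected from the time the participant's parent(s)/legal guardian provide informed consent through the duration of the study". Protocol 8.4.1 says the same and includes AESIs; Protocol 8.4.8 starts AESI collection at signing of the consent document. SAP 6.1.2.1 analyses the safety population (everyone who received the vaccine) and keeps all collected data.

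Protocol 8.10.1 provides for a gap before the dose: "If screening and vaccination are not on the same day", certain procedures must be done on the vaccination day. For children aged 2 to <5 it also covers a serostatus result that is not available the same day. Protocol 5.5 adds temporary delays, for example after short-course systemic steroids: "Study intervention administration should be delayed until systemic corticosteroid use has been discontinued for at least 28 days".

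**The concern.** The SAE and NDCMC estimands are meant to describe children who received one dose at a given dose level. An event that precedes the dose says nothing about the vaccine. Under the present wording it would enter the numerator for the dose the child later received.

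Consider a child who consents, is admitted to hospital while vaccination is on hold, recovers and is then vaccinated. The child belongs to the safety population, and the admission is an SAE recorded during the study. The safety population restricts which children are analysed; it does not restrict which of their events are counted. There is no control arm to show the background rate, and cells of about 20 make a single event visible in the reported percentage.

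**Working it through.** **Step 1. Set the windows side by side.**

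| Item | Collection starts | Start stated for the analysis | Pre-dose exclusion stated |
|---|---|---|---|
| AEs (variable 1) | Consent | Vaccination | Yes, by start time |
| SAEs (7, primary) | Consent | None | No |
| NDCMCs (8, primary) | Consent | None | No |
| AESIs (9, supplementary) | Consent | None | No |
| Tier 1 events (SAP 3.5.2) | Consent | Vaccination | Implied by the window |

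Only variables 7 to 9 lack a start. For AEs, collection also begins at consent, and the SAP corrects for this in the derivation. It makes no such correction for the other three.

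**Step 2. Effect of one pre-dose event.** The plan states no rate for these endpoints, so there is no figure to reproduce. The inputs are the cell sizes (about 20 per age/risk/dose cell; about 40 per dose level in the 5 to <18 stratum) and the SAP's exact Clopper-Pearson method. For x events in n children, the lower limit is the 0.025 quantile of Beta(x, n − x + 1) and the upper limit is the 0.975 quantile of Beta(x + 1, n − x). With x = 0 the lower limit is 0 and the upper limit is 1 − 0.025^(1/n).

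| n | Start at vaccination (x = 0) | As written (x = 1) |
|---|---|---|
| 20 | 0% (0 to 16.8) | 5.0% (0.1 to 24.9) |
| 40 | 0% (0 to 8.8) | 2.5% (0.1 to 13.2) |

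For example, 1 − 0.025^(1/20) = 0.168.

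**Step 3. How likely is one?** The documents give neither the length of the gap nor an SAE rate, so both are assumptions here. Take follow-up as 182 days, the middle of the 175 to 189 day window for Visit 4.

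With a gap of g days, the pre-dose share of the counted time is g/(g + 182): 0% for no gap, 7/189 = 3.7% for 7 days, 14/196 = 7.1% for 14 days and 28/210 = 13.3% for 28 days.

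Let r be the 6-month SAE risk, at a constant rate. One child's pre-dose risk is p = 1 − (1 − r)^(g/182), and the chance of at least one such event among 20 children is 1 − (1 − p)^20.

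| Gap, applied to all 20 children | r = 1% | r = 5% |
|---|---|---|
| 0 days | 0% | 0% |
| 7 days | 0.8% | 3.9% |
| 14 days | 1.5% | 7.6% |
| 28 days | 3.1% | 14.6% |

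These figures are upper readings for each gap, since every child in the cell is given the full gap.

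**The case against.** The strongest case against is that no sentence says pre-dose events are counted. The estimand concerns children who received a dose, the treatment condition is the dose received on Day 1, and Protocol 10.2.1 defines an AE as temporally associated with use of the intervention. It is also fair to say that the rule keeping all collected data sits on the line about intercurrent events and missing data. These points make the window unstated rather than expressly wrong. They do not remove the events: Protocol 8.4.1 and 8.4.1.2 record AEs and SAEs from consent, and no later step takes them out. If a sponsor convention outside the SAP does so, the SAP does not cite it for that purpose; it cites sponsor rules only for missing dates and severity.

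The practical objections stand and limit the size of the problem.

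- The schedule of activities has one combined screening and vaccination visit on Day 1, so the default gap is zero.
- A screen failure ends collection, and rescreening uses a new participant number and a new consent form, so some pre-dose events would never attach to a vaccinated record.
- The stopping rules count events after administration, and the IRC dose-progression reviews use data up to 7 days after vaccination.
- No hypothesis is tested.

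Three stronger readings are tempting, and the documents do not support them.

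- *High-risk children have a longer pre-dose interval.* Nothing says so. Children aged 5 and over need no serostatus test, and the Section 5.5 delays apply to healthy and high-risk children alike.
- *A chronic condition found at the screening examination would count as an NDCMC.* Neither document defines NDCMC beyond its abbreviation, and Protocol 8.3 treats first-visit history and examination as the baseline.
- *All AESI reporting is affected.* Only variable 9 is. The separate Tier 1 analysis in SAP 3.5.2 already starts at vaccination for Guillain-Barré syndrome, acute polyneuropathy, atrial fibrillation and preterm delivery or birth.

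**Conclusion.** The point holds as a gap in the derivation of two primary safety endpoints and one supplementary variable. Followed literally, the SAP attributes to a dose level an SAE or NDCMC that occurred after consent but before that dose.

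The effect is probably small. It needs a gap between consent and dose and an event within it. Under the assumed 6-month SAE risks of 1% to 5%, the chance of at least one such SAE in a cell of 20 is nil with same-day dosing, 0.8% to 3.9% if every child waits 7 days, and 3.1% to 14.6% if every child waits 28 days. The 2 to <5 stratum has the clearest structural reason for a gap. If one event does occur, the reported rate in a cell of 20 rises by 5 percentage points and the upper limit from 16.8% to 24.9%. The stopping rules and dose-progression reviews are not affected.

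**What to change.** In SAP 3.1.1.3, restrict variables 7 to 9 to events with onset (first diagnosis for an NDCMC) at or after vaccination and through the end of the study, with variable 1's rule for same-day events and missing start times. State in the same place how an event with no start date at all is treated, because the SAP does not impute it. Align the wording of SAP 2.2.1.1.3 and 2.2.1.1.4. List events between consent and vaccination separately, so that nothing collected goes unreported.

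The cost is one sentence, two matching edits and one listing. Data collection and study conduct do not change. SAP 2.1 now records no departure from the protocol, so it should note the clarification. The estimand wording in Protocol Section 3, repeated in SAP 2.2, can be aligned at the next amendment.

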#### 3.2. Secondary Endpoint(s)

#### 3.2.1. RSV A- and RSV B-Neutralizing Antibody Titers

RSV A— and RSV B—neutralizing antibody titers will be determined before vaccination and at 1 month after the vaccination visit.

Titers above the LLOQ are considered accurate and their quantitated values will be reported. Refer to Section 5.3.2 for LLOQ details. Titers below the corresponding LLOQ, or denoted as BLQ, will be set to 0.5 × LLOQ for analysis. Missing assay results will not be imputed.

RSV A and RSV B NTs at each blood sampling time point are included in the assay result data, thus no derivation is needed. The following variables will be derived for each participant:

- 1. RSV A/B at each blood sampling time point: This will be derived as the geometric mean of RSV A and RSV B NTs measured at each blood sampling time point for each participant.
- 2. RSV A, RSV B, and RSV A/B NT fold rise: This will be derived from before vaccination to each applicable postvaccination visit. The numerator is the postvaccination value and the denominator is the prevaccination value.

When calculating a fold rise, if assay results are < LLOQ, the assay results will be converted to  $0.5 \times LLOQ$ , except when the prevaccination assay result is < LLOQ while the postvaccination result is  $\geq$  LLOQ, in which case the prevaccination value will be set to LLOQ.

#### 3.2.2. **PBMCs**

Only fold rise from before vaccination to 1 month after vaccination will be derived for each of the PBMC endpoints (RSV F antigen–specific CD4+ T cells secreting IFN $\gamma$  and RSV F antigen–specific CD4+ T cells secreting IL-4).

## 3.3. Other Endpoint(s)

#### 3.3.1. RSV Seroresponse

RSV seroresponse after vaccination will be defined for each participant for Subgroup A and Subgroup B respectively:

- If prevaccination results are ≥ LLOQ, seroresponse is achieved if there is a ≥4-fold rise from prevaccination results.
- If prevaccination results are below LLOQ, seroresponse is achieved if the postvaccination titer is ≥4 × LLOQ.

#### 3.4. Baseline Variables

#### 3.4.1. Baseline Definition

Day 1 is defined as the day of vaccination. Measurements or samples collected prior to vaccination on Day 1 are considered the baseline data for the assessments.

## 3.4.2. Demographics, Baseline, and Medical History

The demographic variables that will be collected include sex, race, ethnicity, and date of birth. Age at the time of vaccination (in years) will be derived based on birthday. For example, if the vaccination date is 1 day before the participant's 6th birthday, the participant is 5 years old. Weight (kg) and height (cm) will be recorded for all participants.

Medical history of clinical significance will be collected and categorized according to the current version (at the time of reporting) of MedDRA.

For participants 2 to <5 years of age, only seropositive participants are included. All participants 5 years of age and older will be considered RSV seropositive and will not require a screening test.

Participants 2 to <18 years of age should either be healthy or be considered by the investigator to be at high risk of RSV disease based on the presence of 1 of the following chronic medical conditions:

- Cystic fibrosis
- Medically treated asthma
- Other chronic respiratory diseases and malformations of the lung
- Down syndrome
- Neuromuscular disease
- Cerebral palsy
- Hemodynamically significant or symptomatic congenital heart disease

